10.3 Dose Reductions for Concomitant CYP Inhibitor Usage

Ruxolitinib is metabolized in the liver by the cytochrome (CYP) P450 metabolizing enzyme system, predominantly by the 3A4 isozyme. With concomitant dosing of potent CYP3A4 inhibitors such as systemic ketoconazole (see Appendix C), plasma exposure of Ruxolitinib increases approximately 2-fold. Thus, a dose reduction of ~ 50% for Ruxolitinib is appropriate for subjects who take systemic ketoconazole or other potent CYP3A4 inhibitors systemically as concomitant medication. BID doses will be decreased to the corresponding once daily dose as follows:

- If dose is 20 mg BID, change dose to 20 mg QD
- If dose is 15 mg BID, change dose to 15 mg QD
- If dose is 10 mg BID, change dose to 10 mg QD
- If dose is 5 mg BID, change dose to 5 mg QD
- If dose is 5 mg QD, no dose change is required.

Potent inhibitors of CYP3A4 include systemic ketoconazole, clarithromycin, itraconazole, nefazodone and telithromycin. NOTE: once the course of therapy using a CYP3A4 inhibitor has been completed, the subject should resume his/her prior BID dose regimen of study drug beginning the next day.

10.4 Dose Reductions for Hepatic Impairment

Hepatic impairment will be classified by the NCI Organ Dysfunction Working Group criteria. Any hepatic dysfunction classified as moderate or severe will require the treating physician to hold study drug until two week after hepatic dysfunction can be classified as mild or normal by NCI criteria. Ruxolitinib may be restarted at 50% of the MTD. If moderate or severe hepatic impairment occur a second time in the same subject, ruxolitinib will be discontinued.

11 ADVERSE EVENTS: REPORTING REQUIREMENTS

The investigator or site staff will be responsible for detecting, documenting and reporting events that meet the definition of an AE or SAE.All Adverse events will be reported to the principle investigator, [name] and study coordinator at [contact].

11.1 Definition of an AE

Any untoward medical occurrence in a subject or clinical investigation subject, temporally associated with the use of a medicinal product, whether or not considered related to the medicinal product. Note: An AE can therefore be any unfavorable and unintended sign (including an abnormal laboratory finding), symptom, or disease (new or exacerbated) temporally associated with the use of a medicinal product. Events meeting the definition of an AE include:

- Exacerbation of a chronic or intermittent pre-existing condition including either an increase in frequency and/or intensity of the condition.
- New conditions detected or diagnosed after investigational product administration even though it may have been present prior to the start of the study.
- Signs, symptoms, or the clinical sequelae of a suspected interaction
- Signs, symptoms, or the clinical sequelae of a suspected overdose of either investigational product or a concomitant medication (overdose per se will not be reported as an AE/SAE). "Lack of efficacy" or "failure of expected pharmacological action" per se within the duration of initial ruxolitinib treatment/exposure of 16 weeks will not be reported as an AE or SAE. However, the signs and symptoms and/or clinical sequelae resulting from lack of efficacy will be reported if they fulfill the definition of an AE or SAE.

Events that **do not** meet the definition of an AE include:

- Medical or surgical procedure (e.g., endoscopy, appendectomy); the condition that leads to the procedure is an AE
- Situations where an untoward medical occurrence did not occur (social and/or convenience admission to a hospital)
- Anticipated day-to-day fluctuations of pre-existing disease(s) or condition(s) present or detected at the start of the study that do not worsen

- The disease/disorder being studied or expected progression, signs, or symptoms of the disease/disorder being studied, unless more severe than expected for the subject's condition.
- Death due to the disease being studied.

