During the Phase I and Phase II development program, ruxolitinib was assessed in healthy volunteers, subjects with various degrees of renal or hepatic impairment, in subjects with rheumatoid arthritis, prostate cancer, multiple myeloma, myelofibrosis (MF), ploycythemia vera and essential thrombocythemia. The aggregate safety database for ruxoltinib included 679 subjects treated in 6 studies. Hematologic events were the most frequently reported adverse events (AE)s however, the majority of these were of Grades 1-2, seldom leading to study drug discontinuation (<1% of subjects). Increased rates of anemia did result in an increase in packed red blood cell (PRBC) transfusion requirements for some ruxolitinib-treated patients but platelet transfusions while on ruxolitinib were rare. No Grade 4 events as it relates to biochemistry laboratory abnormalities of alanine aminotransferase (ALT), aspartate aminotransferase (AST) or cholesterol were reported. The Phase III safety dataset in MF patients shows that it was appropriate to individually adjust doses for patients according to their tolerability and efficacy. However, 124 patients (41.2%) required no dose reduction, indicating the starting dose of 15mg or 20mg BID was appropriate for these individuals. Of the 177 patients who had dose reduction, 91 patients (51%) had only one. Interruptions of dosing were less frequent than dose reductions, with 215 patients (71.4%) requiring no dose interruption. Of the 86 patients who had dose interruptions, 59 patients (19.6%) had only one dose interruption. The Phase III safety dataset in MF subjects showed that the only notable imbalances (ruxolitinib versus placebo or best available therapy [BAT]) in AEs related to hemorrhagic events were in Grade 1-2 skin and soft tissue bruising which did not lead to dose reduction or discontinuation. Similarly, the only notable imbalances (ruxolitinib versus placebo or BAT) in AEs related to infections were urinary tract infections and herpes zoster infections. A thorough QT study was conducted in 50 healthy subjects. There was no indication of a QT/QTc prolonging effect of ruxolitinib in single doses up that exceeded those proposed in this study¹⁶.

Efficacy

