11.4 Laboratory and Other Safety Assessment Abnormalities Reported as AEs and SAEs

Any abnormal laboratory test results (hematology, clinical chemistry, or urinalysis) or other safety assessments (e.g., ECGs, radiological scans, vital signs measurements), including those that worsen from baseline should be recorded as per the NCI-CTC AE criteria. However, these laboratory results are to be recorded as AEs or SAEs if deemed clinically significant in the medical and scientific judgment of the investigator or treating physician. Any clinically significant safety assessments that are associated with the underlying disease are **not** to be reported as AEs or SAEs, except for findings judged by the investigator or treating physician to be more severe than expected for the subject's condition or death. Data will be collected for typical disease-related events such as anemia, leukocytopenia or worsening of

thrombocytopenia. All infections experienced during the study are to be recorded as AEs or SAEs.

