11.5 Disease-Related Events and/or Disease-Related Outcomes Not Qualifying as SAEs

During the study period, the following conditions will not qualify as an AE or SAE provided they are not considered attributable to study medication:

• cases of disease progression.

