11.7 Time Period and Frequency of Detecting AEs and SAEs

The investigator or site staff is responsible for detecting, documenting and reporting events that meet the definition of an AE or SAE. AEs will be collected from the start of Investigational Product and through the follow-up contact. SAEs will be collected over the same time period as stated above for AEs. However, any SAEs assessed **as related** to study participation (e.g., investigational product, protocol mandated procedures, invasive tests, or change in existing therapy) will be recorded from the time a subject consents to participate in the study up to and including any follow-up

contact. All SAEs will be reported to INCYTE [contact] within 24 hours, as indicated.

11.8 Prompt Reporting of Serious Adverse Events and Other Events to the FDA with notification to INCYTE

Any serious adverse events which occur during the clinical study or within 30 days of receiving the last dose of study medication, whether or not related to the study drug, must be reported by the investigator. In addition, any SAEs which occur as a result of protocol specific diagnostic procedures or interventions must also be reported. SAEs brought to the attention of the investigator at any time after cessation of ruxolitinib and considered by the investigator to be related or possibly related to ruxolitinib must be reported to FDA with notification to INCYTE [contact] if and when they occur. Additionally, in order to fulfill international reporting obligations, SAEs that are related to study participation (e.g., procedures, invasive tests, change from existing therapy) or are related to a concurrent medication will be collected and recorded from the time the subject consents to participate in the study until he/she is discharged.

	In	itial Reports		nformation on a ous Report
Type of Event	Time	Documents	Time Frame	Documents
	Frame			
All SAEs	24 hours*	"SAE" data collection	24 hours*	Updated "SAE"
		tool		data collection tool
Pregnancy	2 Weeks*	Pregnancy	2 Weeks*	Pregnancy Follow-
		Notification Form		up Form

• From the time point when the SAE or pregnancy became known to reporter.

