15.4 Safety Analysis

This analysis will include all subjects who have received any protocol treatment, regardless of patient eligibility. The number (%) of subjects with adverse events, serious adverse events, and adverse events leading to treatment discontinuation will be reported. Adverse events summary will be reported by type and severity.

Laboratory parameters will also be summarized using descriptive statistics. The number and proportion of subjects with DLTs will be summarized.

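### Sections 11.1, 11.2, 11.4 and 11.5 conflict on disease-related death and progression, so the AE/SAE counts in 15.4 can understate on-treatment disease deaths and cytopenias

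*Combined protocol and SAP*

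**What the plan says.** Section 11.1 defines an adverse event irrespective of causality, then lists what does not qualify. Two entries matter here: "The disease/disorder being studied or expected progression, signs, or symptoms of the disease/disorder being studied, unless more severe than expected for the subject's condition" and, on a separate line with no qualifier, "Death due to the disease being studied".

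Section 11.2 puts a fatal outcome first among its criteria for a serious event. Its laboratory criterion covers treatment-related grade 4 abnormalities only if they are non-hematologic, although blood dyscrasias appear among its examples of important medical events.

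Section 11.4 keeps significant safety findings linked to CMML itself out of AE and SAE reporting. Its exception reads: "except for findings judged by the investigator or treating physician to be more severe than expected for the subject's condition or death". The same section has abnormal laboratory results recorded by NCI criteria, calls for data on anemia, leukocytopenia and worsening thrombocytopenia, and has every infection recorded as an AE or SAE.

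Section 11.5 says that "the following conditions will not qualify as an AE or SAE provided they are not considered attributable to study medication". The only condition it lists is disease progression.

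Section 11.8 covers serious events during the study or within 30 days of the last dose: these, "whether or not related to the study drug, must be reported by the investigator".

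On known toxicity, Section 2.3 reports: "Hematologic events were the most frequently reported adverse events (AE)s". Section 15.4 tabulates subjects with AEs, SAEs, AEs leading to discontinuation, and DLTs. For the blood counts it says only: "Laboratory parameters will also be summarized using descriptive statistics".

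**The concern.** Safety and tolerability is the first primary objective, and there is no control arm. CMML causes cytopenias (Section 2.1) and so does the drug, so whether a given fall in counts is disease or drug rests on the judgement of an unblinded investigator. Section 6.2 recognises this for DLTs and sets count-based rules for platelets and neutrophils. Sections 11.1 and 11.4 set no such rule for AEs: a finding judged disease-related and no worse than expected is not one.

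If the sections are followed as written, the AE and SAE counts can be biased downward for the toxicity of most interest, and a death from CMML on drug may or may not be reported depending on which section is applied. Routine oversight under Section 17.6 works from adverse event reports: the monitoring committee reviews them monthly and the principal investigator's team every two weeks. An event defined as not an AE can bypass both.

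**Working it through.** **1. The rules side by side**

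| Event | 11.1 | 11.2 | 11.4 | 11.5 |
|---|---|---|---|---|
| Death due to CMML | Not an AE | Serious, by fatal outcome | Apparently reportable | Not addressed |
| Progression of expected severity, judged drug-attributable | Not an AE | No specific rule | No specific rule | Not excluded |
| Progression worse than expected, judged not attributable | Not excluded | No specific rule | No specific rule | Not an AE or SAE |
| Disease-associated cytopenia of expected severity, non-fatal | Not an AE | No hematologic laboratory criterion | Not an AE or SAE | Not addressed |

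Row 1 is a contradiction on death. Rows 2 and 3 give opposite answers because 11.1 tests severity and 11.5 tests attribution. In row 4, 11.1 and 11.4 agree; the issue there is what drops out of the counts, not a conflict.

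Section 11.8 does not settle row 1. It applies to events already classed as serious adverse events, and a reader applying 11.1 would say a CMML death is not an adverse event at all.

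**2. What DLT reporting leaves uncovered**

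Grade 3 cytopenias are not DLTs under 6.2. At grade 4 level, 6.2 requires both a 50% fall from baseline and a count under 25,000/uL (platelets) or 500/uL (ANC). The 50% condition adds something only when half the baseline B lies below the threshold:

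- Platelets: B/2 < 25,000 gives B < 50,000. The entry floor is 35,000 (4.2.1.1), so the range is 35,000 to below 50,000/uL. At B = 35,000, B/2 = 17,500, so counts above 17,500 and below 25,000 are not DLTs. At B = 40,000 the gap is 20,000 to 25,000; at 45,000 it is 22,500 to 25,000.
- ANC: B/2 < 500 gives B < 1,000. The entry floor is 250 (4.2.1.2), so the range is 250 to below 1,000/uL. At B = 600 the gap is 300 to 500; at B = 900 it is 450 to 500.
- Hemoglobin has no 50% condition, so grade 4 anemia remains a DLT.

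**3. Illustrative scale for deaths**

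Inputs: median overall survival 12 to 20 months (2.1); treatment for 16 weeks (Section 7); maximum accrual 53, of whom 29 are in phase 2 (15.2). Assumption: exponential survival from first dose.

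- t = 16 × 7 / 30.4375 = 3.68 months.
- P(death by t) = 1 − 0.5^(t/median).
- Median 12: 1 − 0.5^(3.68/12) = 19.2%, giving 53 × 0.1915 = 10.2 and 29 × 0.1915 = 5.6 deaths.
- Median 20: 1 − 0.5^(3.68/20) = 12.0%, giving 53 × 0.1197 = 6.3 and 29 × 0.1197 = 3.5 deaths.

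These are deaths from any cause. The plan gives no figure of its own to reproduce here.

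**The case against.** Much of the information survives elsewhere.

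- **Cytopenias.** Section 11.4 has abnormal results recorded by NCI criteria and disease-related cytopenia data collected, neither conditional on attribution. CBCs are weekly over the 16 weeks (13.2). Section 15.4 summarises laboratory values and DLTs apart from AEs, and 6.2 reports DLTs through all cycles. A reader might infer that the safety analysis would miss cytopenias altogether; these provisions rule that out. What can go missing is their entry in the AE/SAE counts, and 15.4 names no graded laboratory table, though its wording does not forbid one.
- **Deaths.** A reader might infer that several rules all keep deaths out. Only 11.1 does, and only for deaths due to the disease. Section 11.4's wording on death is ambiguous and concerns safety assessments, but its natural reading makes death an exception; 11.5 does not mention death. Death is a completion category (9.1), a treatment failure (Appendix B) and part of overall survival, with cause followed after discontinuation (10.1). Fatal infections are reportable under 11.4. None of this puts a disease death into the 15.4 counts or the regular AE reviews.
- **MTD.** A reader might infer that dose finding is biased. The MTD rests on DLTs, whose platelet and neutrophil components are count-based, and no route from the AE exclusions to the MTD is shown.
- **Sites.** Section 17.6 mentions other institutions, but Section 11 sends all adverse events to one principal investigator and coordinator, so differing practice between sites is possible rather than demonstrated.

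**Conclusion.** The conflict is in the text and needs correcting. Sections 11.1, 11.2 and 11.4 give different answers on a CMML death, with the caveat that 11.4 is ambiguous. Sections 11.1 and 11.5 give opposite answers on progression whenever severity and attribution diverge. As written, the AE/SAE counts in 15.4 can understate on-treatment disease deaths and cytopenias judged disease-related: mainly grade 3 events, and grade 4-level counts that miss the 50%-fall rule in the baseline ranges worked out above. The other summaries compensate only partly, because 15.4 plans neither an on-treatment death count nor a table by worst grade.

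The size of the understatement cannot be derived from the documents. The 12-19% (about 6-10 of 53) is an illustrative upper range for deaths in the first 16 weeks. It applies a background median exponentially from entry, although eligibility requires life expectancy above 3 months (4.1.8), and it treats everyone as on drug throughout, although progression leads to discontinuation (9.3). It says nothing about cause. A reader might infer that most such deaths would be called disease deaths; the documents give no basis for that share.

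**What to change.** 1. Reconcile 11.1, 11.2, 11.4, 11.5 and 11.8 into one rule: every death from first dose to 30 days after last dose, the window 11.8 already uses, is reported with its recorded cause whatever the attribution.
2. Apply a single test to disease progression, stated once and used in both 11.1 and 11.5.
3. In 15.4 add a count of deaths on treatment or within 30 days of last dose, in all treated subjects.
4. In 15.4 add a table of shift from baseline to worst on-treatment CTCAE v4.0 grade for hemoglobin, platelets and ANC, irrespective of attribution.

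The cost is amendment wording and two tables from CBC and vital-status data already collected. The downside is a few more SAE forms for disease deaths and a less favourable-looking cytopenia table. No dosing rule or DLT definition changes.

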11.2 Definition of an SAE

A serious adverse event is any untoward medical occurrence that, at any dose:

- Results in death
- Is life-threatening

NOTE: The term "life-threatening" the definition refers to an event in which the subject was at risk of death at the time of the event. It does not refer to an event, which hypothetically might have caused death, if it were more severe.

Requires hospitalization or prolongation of existing hospitalization.

NOTE: In general, hospitalization signifies that the subject has been detained (usually involving at least an overnight stay) at the hospital or emergency ward for observation and/or treatment that would not have been appropriate in the physician's office or out-patient setting. Complications that occur during hospitalization are AEs. If a complication prolongs hospitalization or fulfills any other serious criteria, the event is serious. When in doubt as to whether "hospitalization" occurred or was necessary, the AE should be considered serious. Hospitalization for elective treatment of a pre-existing condition that did not worsen from baseline is not considered an AE.

Results in disability/incapacity

NOTE: The term disability means a substantial disruption of a person's ability to conduct normal life functions. This definition is not intended to include experiences of relatively minor medical significance such as uncomplicated headache, nausea, vomiting, diarrhea, influenza, and accidental trauma (e.g. sprained ankle) which may interfere or prevent everyday life functions but do not constitute a substantial disruption.

- Is a congenital anomaly/birth defect
- All treatment related grade 4 non-hematologic laboratory abnormalities assessed using the National Cancer Institute (NCI) Common Terminology Criteria for Adverse Events (CTCAE) v 4.0.

Medical or scientific judgment should be exercised in deciding whether reporting is appropriate in other situations, such as important medical events that may not be immediately life-threatening or result in death or hospitalization but may jeopardize the subject or may require medical or surgical intervention to prevent one of the other outcomes listed in the above definition. These should also be considered serious. Examples of such events are invasive or malignant cancers, intensive treatment in an emergency room or at home for allergic bronchospasm, blood dyscrasias or convulsions that do not result in hospitalization, or development of drug dependency or drug abuse.

11.3 Relationship to Investigational Product

It is a regulatory requirement for investigators to assess relationship to investigational product based on information available. The assessment should be reviewed on receipt of any new information and amended if necessary. "A reasonable possibility" is meant to convey that there are facts/evidence or arguments to suggest a causal relationship. Facts/evidence or arguments that may support "a reasonable possibility" include, e.g., a temporal relationship, a pharmacologically-predicted event, or positive dechallenge or rechallenge. Confounding factors, such as concomitant medication, a concurrent illness, or relevant medical history, should also be considered.

11.4 Laboratory and Other Safety Assessment Abnormalities Reported as AEs and SAEs

Any abnormal laboratory test results (hematology, clinical chemistry, or urinalysis) or other safety assessments (e.g., ECGs, radiological scans, vital signs measurements), including those that worsen from baseline should be recorded as per the NCI-CTC AE criteria. However, these laboratory results are to be recorded as AEs or SAEs if deemed clinically significant in the medical and scientific judgment of the investigator or treating physician. Any clinically significant safety assessments that are associated with the underlying disease are **not** to be reported as AEs or SAEs, except for findings judged by the investigator or treating physician to be more severe than expected for the subject's condition or death. Data will be collected for typical disease-related events such as anemia, leukocytopenia or worsening of

thrombocytopenia. All infections experienced during the study are to be recorded as AEs or SAEs.

11.5 Disease-Related Events and/or Disease-Related Outcomes Not Qualifying as SAEs

During the study period, the following conditions will not qualify as an AE or SAE provided they are not considered attributable to study medication:

• cases of disease progression.

